8.0 Dosage Modification Based on Adverse Events

Strictly follow the modifications in this table for the first **two** cycles, until individual treatment tolerance can be ascertained. Individual drugs can be dose reduced as per the table below depending on the adverse event attribution. Thereafter, these modifications should be regarded as guidelines to produce mild-to-moderate, but not debilitating, side effects. If multiple adverse events are seen, administer dose based on greatest reduction required for any single adverse event observed. Reductions apply to treatment given in the preceding cycle and are based on adverse events observed since the prior dose.

NOTE: If either of pomalidomide or ixazomib is discontinued, the patient can continue on the other drugs, unless specified otherwise in the dose modification tables. If both are discontinued, the patient will go to event monitoring (Section 18.0).

ALERT: ADR reporting may be required for some adverse events (See Section 10)

8.1 Dose Levels for each drug in the combination (Based on Adverse Events in Tables 8.2-4)

NOTE: One drug can be reduced each time based on the drug most likely related to the toxicity observed.

Ixazomib (Days 1, 8, 15)		Pomalidomide (Day 1-21)		Dexamethasone (Days 1, 8, 15, 22)	
Starting dose	4 mg	Starting dose	4 mg	Starting dose	40 mg
-1	3 mg	-1	3 mg	-1	20 mg
-2	2.3 mg	-2	2 mg	-2	12 mg
-3	2.3 mg days 1, 15	-3	1 mg	-3	4 mg
-4	Discontinue	-4	Discontinue	-4	Discontinue

If patients cannot tolerate dose level – 3 of ixazomib AND pomalidomide they will go to event monitoring per Section 18.0. If dexamethasone is discontinued, the patient may continue treatment.

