8.2 Dose modifications for ixazomib based on adverse events during a cycle

CTCAE System/Organ/Class (SOC)	ADVERSE EVENT	AGENT[#]	ACTION**
Investigations	If platelet count $<30 \times 10^9/L$ or ANC $<1.0 \times 10^9/L$ or ANC $>1.0 \times 10^9/L$ (up to LLN) with fever (temperature $>38.5^\circ C$)	Ixazomib	Days 2-15: Ixazomib dose should be omitted. Complete blood count (CBC) with differential should be followed weekly. If ANC is $\geq 1.0 \times 10^9/L$ and/or platelet counts $\geq 30 \times 10^9/L$, ixazomib may be reinitiated with 1 dose level reduction (see Table 8.1). The subsequent cycle will use the reduced dose.
Skin and subcutaneous tissue disorders	Rash, maculopapular, \geq Grade 2	Ixazomib	Omit ixazomib till rash resolves to \leq Grade 1 (See Section 9.9a). Restart at same dose. If the rash recurs, reduce dose by one dose level.
	Any skin, Grade 4		Discontinue ixazomib
Nervous System Disorders	Newly developed Grade 1 peripheral neuropathy with pain, \geq Grade 2 peripheral neuropathy,	Ixazomib	Reduce dose of ixazomib to the next lower dose level
	Grade 2 neuropathy with pain or Grade 3 peripheral neuropathy	Ixazomib	Omit ixazomib until toxicity resolves or returns to baseline. When toxicity resolves, re-initiate ixazomib at the next lower dose level.

Table 8.2			
CTCAE System/Organ/Class (SOC)	ADVERSE EVENT	AGENT[#]	ACTION^{**}
	Grade 4 peripheral neuropathy	Ixazomib	Omit ixazomib. Peripheral neuropathy should be monitored until toxicity resolves or returns to baseline. Upon recovery, if the patient has received clinical benefit from therapy with ixazomib, the investigator may consider restarting ixazomib at the next lower dose level.
Other	Any other non-hematological Grade 3 attributable toxicity except: Grade 3 nausea and/or emesis in the absence of optimal anti-emetic prophylaxis Grade 3 diarrhea that occurs in the absence of optimal supportive therapy Grade 3 fatigue	Ixazomib Pomalidomide	Omit ixazomib or pomalidomide or both depending on the attribution to either or both drugs, until resolution to Grade ≤ 1 or baseline Restart at next lower dose - If a patient is already at the lowest drug level, go to event monitoring If the toxicity can be attributed to either of the drugs, pomalidomide should be discontinued at first instance followed by ixazomib for recurrence of the same toxicity necessitating dose modification

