	Grade 4 Nonhematologic Toxicities	Ixazomib Pomalidomide	Permanently discontinue pomalidomide. Consider permanently discontinuing ixazomib – Exception if the investigator determines the patient is obtaining a clinical benefit If both ixazomib and pomalidomide are discontinued, the patient will go to event monitoring

* Located [REDACTED]

** Use the following to describe actions in the Action column:

- Omit = The current dose(s) for the specified drug(s) during a cycle is skipped. The patient does not make up the omitted dose(s) at a later time
- Hold/Delay = The current dose(s) of all drugs during a cycle is delayed. The patient does make up the delayed dose(s) when the patient meets the protocol criteria to restart drugs.
- Discontinue = The specified drug(s) are totally stopped.

NOTE: For toxicities attributable to both ixazomib and pomalidomide, only one of the drugs should be reduced for each incidence of toxicity severe enough to necessitate dose reduction. The drug reduced should alternate starting with pomalidomide for the first dose reduction.

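### For other non-hematological Grade 3 toxicity, one cell of Table 8.2 both restarts the drug one level down and stops pomalidomide outright

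*Combined protocol and SAP*

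**What the plan says.** The row concerned is the one in Table 8.2 (Section 8.2) for non-hematological Grade 3 toxicity not covered elsewhere in the table. It names both ixazomib and pomalidomide, and its action cell gives these instructions in turn:

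- "Omit ixazomib or pomalidomide or both depending on the attribution to either or both drugs", until the event has settled to Grade 1 or less or to baseline;
- "Restart at next lower dose", with a move to event monitoring for a patient already at the lowest level;
- where the toxicity can be put down to either drug, "pomalidomide should be discontinued at first instance followed by ixazomib for recurrence of the same toxicity necessitating dose modification".

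The key under the table fixes the vocabulary of the action column: "Omit = The current dose(s) for the specified drug(s) during a cycle is skipped" and "Discontinue = The specified drug(s) are totally stopped". The NOTE below the key deals with toxicity attributed to both drugs. It says that "only one of the drugs should be reduced for each incidence of toxicity severe enough to necessitate dose reduction" and that "The drug reduced should alternate starting with pomalidomide for the first dose reduction". Section 8.1 has its own note: "One drug can be reduced each time based on the drug most likely related to the toxicity observed".

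Section 8.0 makes the modifications strict for the first two cycles and treats them as guidelines afterwards. It lets a patient stay on the remaining drugs if one of ixazomib and pomalidomide is discontinued, and sends the patient to event monitoring if both are.

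**The concern.** After a single event, a drug cannot be both totally stopped and restarted one level lower. A site that follows the defined term ends pomalidomide for good. A site that follows the restart instruction brings the drug back at a reduced dose. Each can point to the same cell, and in the first two cycles each is told to follow it strictly. What is at stake is whether patients with the same event receive the same treatment, and whether a patient remains on the three-drug regimen that the trial is meant to evaluate.

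**Working it through.** This is a textual check. No sample size, error rate or event count enters, and the plan gives no figure to reproduce. The only arithmetic is a count of steps on the dose ladder in Section 8.1.

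**Step 1. Set the passages side by side.**

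| Place | Which toxicity | Action for pomalidomide |
|---|---|---|
| Table 8.2 cell, opening instructions | Other non-hematological Grade 3, attributed to either or both drugs | Omit if attributed, then restart one level down |
| Table 8.2 cell, last sentence | Same row, attributable to either drug | Discontinue at the first instance; ixazomib follows if the same toxicity recurs |
| Table 8.2 NOTE | Attributable to both drugs | One drug reduced per incidence, alternating, pomalidomide first |
| Section 8.1 note | Any | One drug reduced each time, the one most likely responsible |
| Table 8.3, other non-hematologic, Grade 3 or higher | Grade 3 or higher | Omit, then restart one level down |
| Table 8.2, Grade 4 row | Grade 4 non-hematologic | Permanent stop |

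**Step 2. Can the key reconcile the cell?** No. Discontinuing and omitting are separate entries, and only omitting is compatible with a later restart.

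**Step 3. Can scope reconcile it?** The NOTE speaks of both drugs and the last sentence of either drug, so those two might be said to address different cases. That does not help within the cell, because the omit-and-restart instruction expressly covers attribution to either drug as well as to both.

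**Step 4. Compare with neighbouring rules.** Read literally, the last sentence gives pomalidomide the same action at Grade 3 as the Grade 4 row does. It also departs from the matching Table 8.3 row, which differs from the Table 8.2 cell in its recovery threshold too: Grade 2 or less for restarting pomalidomide, against Grade 1 or less or baseline.

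**Step 5. Count the consequence.** Section 8.1 gives each drug a starting dose, levels -1, -2 and -3, and level -4, which is discontinuation. Assume a patient at full dose of both drugs, with no other modifications and every event falling in this row.

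- *Literal reading.* First instance: pomalidomide goes from 4 mg to none. Recurrence of the same toxicity: ixazomib stops too. Both drugs are off after 2 instances, and Section 8.0 sends the patient to event monitoring.
- *Reduction reading.* This takes the one-level step from the cell and the alternation from the NOTE; neither passage states both. First instance: pomalidomide goes from 4 mg to 3 mg. After n instances pomalidomide has been lowered n/2 times, rounded up, and ixazomib n/2 times, rounded down. At n = 6 that is 3 and 3, so both are at level -3. The patient leaves treatment at n = 7 under the cell's rule on already being at the lowest level, or at n = 8 if both must reach level -4 (4 and 4).

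The two readings therefore differ by one drug after the first instance, and in duration of treatment by 2 instances against 7 or 8.

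**The case against.** The strongest reply is that this is a slip of wording which a careful site would see through. The disputed sentence closes by speaking of dose modification, which suits an instruction about the order in which drugs are adjusted. The NOTE gives the same order and speaks of reducing. Section 8.1 and the matching Table 8.3 row also point to reduction. Where Table 8.2 plainly wants a lasting stop in this block, the Grade 4 row says so with the word permanently. This is a fair account of what may have been meant, but it is not conclusive. Discontinue is a defined term for that column, and the literal reading is workable because Section 8.0 allows treatment to continue on the remaining drugs.

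The reply does succeed in limiting the point:

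- **Scope.** A reader might infer that any first Grade 3 event ends pomalidomide. The documents do not support that. The row excludes Grade 3 fatigue, and nausea, emesis or diarrhea occurring without optimal supportive care. Cytopenias, maculopapular rash and neuropathy have rows of their own. The last sentence also needs attribution to either drug, and ixazomib follows only if the same toxicity recurs.
- **The NOTE.** A reader might take the NOTE to prescribe omission and one-level reductions. It says only that one drug is reduced and that the choice alternates, and only for toxicity attributed to both drugs. Omission and the next lower dose come from the cell, so the NOTE is supporting evidence rather than the core of the conflict.
- **Primary endpoint.** A reader might infer that early loss of pomalidomide lowers the confirmed response rate. Section 16.11 does require response on two consecutive evaluations, so an effect is possible. But the documents give neither the frequency of these events nor the effect of dropping pomalidomide on confirmation. Patients may continue on the other drugs, and footnote a to Table 11.5 accepts two consecutive assessments at any time before new therapy.

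**Conclusion.** The contradiction stands as an internal inconsistency in one Table 8.2 cell, measured against that table's own key, and it should be corrected. The NOTE, the Section 8.1 note and the matching Table 8.3 row also fail to match a total stop. For a patient still at the starting dose, the first qualifying event leads either to no pomalidomide or to 3 mg; for a patient already reduced, the alternative is the next level down from there. The ladder count rests on the assumptions in Step 5.

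The risk is that sites handle the same event differently. It is sharpest in the first two cycles, when the table binds; afterwards the table only guides. Any consequence for the confirmed response rate or for the final decision is unquantified, and the point does not depend on it.

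**What to change.** The sponsor should state which action is intended for these events and reword the cell so that a single term from the key applies. The revision should be checked against the NOTE, the Section 8.1 note and the Table 8.3 row for other non-hematologic toxicity. That check should cover the differing recovery thresholds. It should also cover the fact that the Table 8.3 row has no upper grade limit, whereas Table 8.2 treats Grade 4 separately. The cost is a short wording amendment, in one cell or a few lines if Table 8.3 is aligned as well, plus notice to sites. Sample size, decision rules and analyses are untouched. If patients have already been treated under this wording, a listing of such events with the action taken would show whether sites differed.

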8.11 Instruction for initiation of a new cycle of therapy

A new cycle of treatment may begin on the scheduled Day 1 of a new cycle if:

- The ANC is $\geq 1000/\mu\text{L}$
- The platelet count is $\geq 50,000/\mu\text{L}$
- Any other non-hematologic treatment -related adverse event that may have occurred has resolved to \leq Grade 1 or baseline severity.

If these conditions are not met on Day 1 of a new cycle, the subject will be evaluated weekly and a new cycle of therapy will be held until the toxicity has resolved as described above.

If any drug dosing was halted during the previous cycle and was restarted with a one-level dose reduction without requiring an interruption for the remainder of the cycle, then that reduced dose level will be initiated on Day 1 of the new cycle.

If any drug dosing was omitted for the remainder of the previous cycle or if the new cycle is held due to known hematologic toxicity newly encountered on the scheduled Day 1, then the new cycle will be started with a one-level dose reduction. If a new cycle of therapy cannot be restarted within 4 weeks of the scheduled Day 1 due to non-resolution of drug related toxicities, the patient will be removed from protocol therapy and will go to event monitoring.

→ → Use the NCI Common Terminology Criteria for Adverse Events (CTCAE) version 4.0* unless otherwise specified ← ←

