Immune system disorders	Allergic reaction Grade 2-3	Pomalidomide	
 Omit dose and follow at least weekly If the toxicity resolves to \leqGrade 1 prior to Day 15 restart at next lower dose level and continue the cycle until Day 21
	Grade 4	Pomalidomide	
 Discontinue pomalidomide and remove patient from all study treatment
Vascular disorders	Thromboembolic event \geq Grade 3	Pomalidomide	
 Omit dose and start anticoagulation Restart at investigator's discretion (maintain dose level)
Endocrine disorders	Hyperthyroidism or Hypothyroidism \geq grade 2	Pomalidomide	
 Omit pomalidomide for remainder of cycle, evaluate etiology, and initiate appropriate therapy See Instructions for Initiation of a New Cycle and reduce the dose of pomalidomide by 1 dose level
Other non-hematologic adverse event	Other non-hematologic toxicity \geq Grade 3	Pomalidomide	
 Omit pomalidomide dose. Follow at least weekly If the toxicity resolves to \leqGrade 2 prior to Day 21, restart pomalidomide at next lower dose level and continue the cycle through Day 21

* Located at [REDACTED]

** Use the following to describe actions in the Action column:

- Omit = The current dose(s) for the specified drug(s) during a cycle is skipped. The patient does not make up the omitted dose(s) at a later time
- Hold/Delay = The current dose(s) of all drugs during a cycle is delayed. The patient does make up the delayed dose(s) when the patient meets the protocol criteria to restart drugs.
- Discontinue = The specified drug(s) are totally stopped.

NOTE: For toxicities attributable to both ixazomib and pomalidomide, only one of the drugs should be reduced for each incidence of toxicity severe enough to necessitate dose reduction. The drug reduced should alternate starting with pomalidomide for the first dose reduction.

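### For a Grade 4 non-hematologic event in Table 8.3's residual row, Table 8.2 stops pomalidomide for good while Table 8.3 restarts it one level lower on recovery, and no text says which governs

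*Combined protocol and SAP*

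**What the plan says.** Table 8.2 is headed as the ixazomib table, but its Grade 4 non-hematologic row lists both ixazomib and pomalidomide as agents. The action is "Permanently discontinue pomalidomide. Consider permanently discontinuing ixazomib", with an exception for clinical benefit after the ixazomib sentence. The footnote leaves no room for a later restart: "Discontinue = The specified drug(s) are totally stopped".

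Table 8.3 has its own Grade 4 rows for rash, sensory neuropathy and allergic reaction, and each of them stops pomalidomide. Non-hematologic events without a named row fall under "Other non-hematologic toxicity" at Grade 3 or higher, so Grade 4 is included. The action there is to omit the dose, follow the patient at least weekly and, if the event resolves to Grade 2 or less "prior to Day 21, restart pomalidomide at next lower dose level and continue the cycle through Day 21".

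Section 8.11 covers the case where dosing was omitted for the rest of a cycle: "then the new cycle will be started with a one-level dose reduction". A new cycle requires that "Any other non-hematologic treatment -related adverse event that may have occurred has resolved to" Grade 1 or less, or baseline. It also sets an outer limit, beyond which protocol therapy ends: "If a new cycle of therapy cannot be restarted within 4 weeks of the scheduled Day 1 due to non-resolution of drug related toxicities".

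Section 8.0 makes the modifications strict for the first two cycles and guidelines after that.

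**The concern.** Two binding instructions for the same drug after the same event cannot both be followed. A site working from Table 8.3 may re-expose a patient to pomalidomide after a Grade 4 toxicity, when another table in the same section says that patient should never receive it again. In Cycles 1 and 2 the site has no stated discretion to choose between them. What is at stake is patient safety and uniform treatment across sites.

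**Working it through.** The plan states no figure on this point, so the check is a comparison of texts plus the dose arithmetic.

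**1. Does one event fall under both rows?** Yes. Table 8.2's row takes every Grade 4 non-hematologic toxicity. Table 8.3's residual row takes any that is not rash, sensory neuropathy, allergic reaction, thromboembolism or thyroid disorder. Pneumonia and acute renal failure, both listed in Section 15.27 as very common with pomalidomide, have no named row in Table 8.3 and would land there.

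**2. What happens to pomalidomide?**

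| Course of the Grade 4 event | Table 8.2 | Table 8.3 with Section 8.11 |
|---|---|---|
| Falls to Grade 2 or less before Day 21 | Stopped permanently | Restart one level lower in the same cycle |
| Pomalidomide omitted for the rest of the cycle; Grade 1 or less, or baseline, reached within 4 weeks of the scheduled Day 1 | Stopped permanently | Next cycle starts one level lower |
| Neither | Stopped permanently | Patient leaves protocol therapy |

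The tables disagree in the first two lines. In the third, pomalidomide ends either way.

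**3. Size of the difference for one patient.** Using the dose levels in Table 8.1 and 21 dosing days per cycle:
- Starting dose: 4 mg × 21 = 84 mg per cycle.
- Table 8.3 after recovery: 3 mg × 21 = 63 mg per full cycle.
- Table 8.2: 0 mg in every later cycle.

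The same split occurs from 3 mg (2 mg against 0) and from 2 mg (1 mg against 0). From 1 mg the next level is discontinuation, so the tables agree.

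**4. Does any text rank the tables?**
- Section 8.0's instruction to take the largest reduction is worded for several adverse events, not for one event listed in two tables.
- Section 8.0's attribution sentence selects the drug to reduce. It does not say which table applies. If attribution did divide the tables, an ixazomib-related event would end pomalidomide permanently while a pomalidomide-related one would allow a restart. No text says that.
- The note under both tables says "The drug reduced should alternate starting with pomalidomide for the first dose reduction". It chooses a drug and is silent on stopping versus restarting.
- The clinical-benefit exception follows the ixazomib sentence. Even if it were read to cover both drugs, Table 8.3's restart does not require benefit.

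**5. Related mismatch at Grade 3.** For other Grade 3 non-hematologic toxicity attributed to pomalidomide:
- Table 8.2 restarts at Grade 1 or less, or baseline. Table 8.3's residual row restarts within the cycle at Grade 2 or less, although its rash, sensory neuropathy and allergic reaction rows require Grade 1 or less.
- Table 8.2 exempts fatigue, and nausea, emesis or diarrhea without optimal supportive care. Table 8.3 exempts nothing.

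**The case against.** The best defence is that a careful site would follow Table 8.2 anyway: its row is specific to Grade 4, names pomalidomide and says the stop is permanent, whereas Table 8.3's row is a catch-all. Section 8.0's preference for the largest reduction leans the same way. That is a fair guess at intent, but it is inference. Table 8.3 may equally have meant to allow rechallenge, since its thromboembolic and thyroid rows permit resumption with no upper grade limit.

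It also stands that the conflict is narrow. It needs a Grade 4 residual-row event that resolves in time, and after Cycle 2 the tables are only guidelines. Safeguards exist: the review of dose-limiting toxicity in the first 6 patients, the adverse event stopping rule in Section 16.52, and withdrawal by the investigator under Section 13.4. These limit harm across the trial, but none tells a site which table to apply to the patient in front of it.

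Two stronger readings are tempting and not supported:
- A reader might take the Section 16.52 trigger of 5 in the first 15 as capping these events at 4 of 15. That rule counts only events at least possibly related to treatment, while Table 8.2's Grade 4 row has no attribution condition. It also counts Grade 5 events, later cycles and events with their own rows.
- A reader might extend the conflict to Grade 4 sensory neuropathy, where Table 8.3 ends all treatment and Table 8.2 leaves an ixazomib restart open. Those rows name different drugs, so the difference may simply follow attribution.

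**Conclusion.** The protocol is wrong as written on this point. For a Grade 4 residual-row event that resolves in time, pomalidomide is either stopped permanently or resumed one level lower (from the start, 0 mg against 3 mg daily on Days 1–21), and no rule decides between them. It should be fixed on patient-safety grounds, but it is a clarification and does not undermine the design.

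How often it would arise cannot be stated. The documents give no rate of such events for this regimen. The nearest figure, 8% Grade 3 or 4 pneumonia in the pomalidomide–dexamethasone study described in Section 1.5, pools two grades and comes from a two-drug regimen with pomalidomide at 2 mg daily. It shows that residual-row events are plausible and no more. Any probability built on an assumed rate would also have to allow for resolution in time, for which no figure is given.

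A reader might infer that divergent dosing biases the response rate. Nothing in the documents shows this, and no effect on the primary endpoint, alpha, power or sample size is claimed.

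The conclusion rests on reading the residual row's grade limit as including Grade 4, and on the absence of any ranking text in Section 8 or Section 13.

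**What to change.** 1. **Grade 4.** Change Table 8.3's residual row to Grade 3 only, and refer Grade 4 events at least possibly related to pomalidomide to Table 8.2. Permanent discontinuation then governs unless the clinical team deliberately amends that row. State in Table 8.2's Grade 4 row that the action on each drug follows attribution:
   - Events attributed to ixazomib alone act on ixazomib.
   - Events attributed to dexamethasone alone follow Table 8.4. Five of its rows have no upper grade limit and keep pomalidomide going (for example pancreatitis of Grade 3 or higher), so the Grade 4 row needs this qualifier.
   - Events unrelated to any study drug are handled by omitting doses until recovery, at the investigator's discretion.

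2. **Grade 3.** For other non-hematologic toxicity attributed to pomalidomide, use Table 8.2's restart threshold (Grade 1 or less, or baseline, as in Section 8.11) and its exemptions in both tables. Where either drug could be the cause, apply the existing note: reduce one drug, starting with pomalidomide. Table 8.2's Grade 3 row instead has pomalidomide stopped the first time such a toxicity occurs. Amend it to match the note.

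The cost is a protocol amendment and a site memo. Patients who recover from a related Grade 4 residual-row event lose the reduced-dose pomalidomide rechallenge. Some Grade 3 patients will wait longer to restart, while the exempted Grade 3 events will no longer call for omission under Table 8.3. There is no statistical cost.

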8.3 Dose modifications for pomalidomide based on adverse events during a cycle

Table 8.3			
CTCAE System/Organ/Class (SOC)	ADVERSE EVENT	AGENT	ACTION**
Blood and lymphatic system disorders	Febrile neutropenia associated with fever ($\geq 38.5^{\circ}\text{C}$)	Pomalidomide	
 • Omit pomalidomide dose. • Follow CBC weekly. • If neutropenia has resolved to \leqGrade 2 prior to Day 21 and fever has resolved, restart pomalidomide at next lower dose level and continue the cycle through Day 21 • If febrile neutropenia is the only toxicity for which a dose reduction is required G-CSF may be used and the pomalidomide dose maintained
Investigations	Grade 3 neutrophil decreased and sustained for 7 days or Grade 4 neutropenia Platelet count decreased \geq Grade 3 (platelet count $< 50,000/\text{mm}^3$)	Pomalidomide	
 • Omit pomalidomide dose. • Follow CBC weekly. • Hold anticoagulation until platelets $\geq 50,000/\text{mm}^3$ • If platelet count resolves to \leqGrade 2 prior to Day 21, restart pomalidomide at next lower dose level and continue the cycle through Day 21 • If neutropenia has resolved to \leqGrade 2 prior to Day 21, restart pomalidomide at next lower dose level and continue the cycle through Day 21 • If neutropenia is the only toxicity for which a dose reduction is required G-CSF may be used and the pomalidomide dose maintained
Skin and subcutaneous tissue disorders	Rash maculopapular Grade 2 or 3	Pomalidomide	
 • Omit pomalidomide dose; follow weekly • If the toxicity resolves to \leqGrade 1 prior to Day 21, restart pomalidomide at next lower dose level and continue the cycle through Day 21
	Any rash Grade 4	Pomalidomide	
 • Discontinue pomalidomide and remove patient from all study treatment
Nervous system disorders	Peripheral sensory neuropathy Grade 3	Pomalidomide	
 • Omit pomalidomide dose and follow at least weekly • If the toxicity resolves to \leqGrade 1 prior to Day 21, restart pomalidomide at next lower dose level and continue the cycle through Day 21

Table 8.3			
CTCAE System/Organ/Class (SOC)	ADVERSE EVENT	AGENT	ACTION**
	Grade 4	Pomalidomide	
 Discontinue pomalidomide and remove patient from all study treatment

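### Tables 8.2 and 8.3 give incompatible pomalidomide instructions for the same Grade 4 non-hematologic event, and in cycles 1 and 2 both are binding

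*Combined protocol and SAP*

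**What the plan says.** Section 8.0 introduces the dose-modification tables with "Strictly follow the modifications in this table for the first" two cycles; after that they are guidelines. It also lets the choice of drug to reduce depend on attribution.

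Table 8.2 is headed as the ixazomib table, but its Grade 4 non-hematologic row names both ixazomib and pomalidomide as agents. The order is "Permanently discontinue pomalidomide. Consider permanently discontinuing ixazomib", followed by an exception for patients who are benefiting clinically. The key under the table defines discontinuing as stopping the drug completely.

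Table 8.3, the pomalidomide table, ends with a row for other non-hematologic toxicity of Grade 3 or higher. It says to omit pomalidomide, follow at least weekly and, on recovery to Grade 2 or less before Day 21, "restart pomalidomide at next lower dose level and continue the cycle through Day 21". Omitting is defined as skipping the current dose.

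Section 8.11 carries this forward. If the drug was restarted lower within the cycle, "then that reduced dose level will be initiated on Day 1 of the new cycle". If it was omitted for the rest of the cycle, "then the new cycle will be started with a one-level dose reduction". A new cycle requires non-hematologic related events to be at Grade 1 or less or at baseline. If it cannot start within 4 weeks of the scheduled Day 1 because drug-related toxicity has not resolved, the patient leaves protocol therapy.

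**The concern.** Grade 4 lies inside the Grade 3-or-higher range of the Table 8.3 row, so one event attributed to pomalidomide can trigger a permanent stop under one table and a lower-dose restart under the other. A site cannot do both. In cycles 1 and 2, when adherence must be strict, one site could end pomalidomide for good while another gives it again in the same cycle, each following a stated rule. At stake are re-exposure after a Grade 4 event and uniform delivery of the regimen across sites.

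The affected events are plausible. Section 15.27 lists pneumonia and acute renal failure among the very common pomalidomide toxicities (10% or more), and neither has a row in Table 8.2 or 8.3. In the 60-patient pomalidomide-dexamethasone study described in Section 1.5, Grade 3 or 4 pneumonia occurred in 8%. Grade 4 alone and attribution are not given, so this shows plausibility and is not a rate.

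**Working it through.** The plan states no figure to reproduce. The check sets the rows side by side and then works out the planned dose.

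**1. Which events meet both rows.** Table 8.3 has separate Grade 4 rows for rash, peripheral sensory neuropathy and allergic reaction, each with "Discontinue pomalidomide and remove patient from all study treatment". Thromboembolic and thyroid events also have rows of their own. Every other Grade 4 non-hematologic event attributed to pomalidomide falls into Table 8.3's catch-all and also into Table 8.2's Grade 4 row. That includes motor neuropathy and skin events other than rash, because Table 8.2's specific rows for those name ixazomib only.

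**2. Whether another rule decides.**
- The greatest-reduction rule in Section 8.0 applies when several adverse events are seen, not when one event has two rows.
- The NOTE under both tables says that "only one of the drugs should be reduced for each incidence of toxicity severe enough to necessitate dose reduction". It concerns toxicity attributable to both drugs, and it chooses the drug, not the row.
- The clinical-benefit exception follows the ixazomib clause. If it were stretched to pomalidomide, patients without benefit would still face both orders.
- Section 13.4 allows an investigator to stop treatment for an adverse event but does not require it.

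**3. Timing.** Under Table 8.3 with Section 8.11:
- Grade 2 or less before Day 21: restart one level lower in the same cycle.
- Later recovery to Grade 1 or less or baseline, within 4 weeks of the scheduled Day 1: start the next cycle one level lower.
- Not resolved within that limit: off protocol therapy, so pomalidomide ends under either table.

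**4. Planned pomalidomide in the next full cycle, once that cycle may start.** Inputs: Days 1-21 (Table 7.1); dose levels 4, 3, 2 and 1 mg, then discontinue (Table 8.1). Formula: dose one level lower × 21 days.

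| Dose at event | Table 8.2 | Table 8.3 with 8.11 |
|---|---|---|
| 4 mg | 0 mg | 3 × 21 = 63 mg |
| 3 mg | 0 mg | 2 × 21 = 42 mg |
| 2 mg | 0 mg | 1 × 21 = 21 mg |
| 1 mg | 0 mg | discontinue = 0 mg |

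**5. Grade 3.** For Grade 3 events within both catch-all rows, Table 8.2 withholds the drug until Grade 1 or less or baseline, while Table 8.3 accepts Grade 2 or less. Section 8.11 uses the stricter threshold for starting a cycle.

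**The case against.** The best defence is that the conflict is narrow. After cycle 2 the tables are only guidelines, so two binding orders collide only in cycles 1 and 2. Unresolved toxicity ends pomalidomide under either table. Both points stand and limit the finding.

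A reader might infer that the adverse event stopping rule in Section 16.52 is affected. It is not: a patient is counted once a related Grade 4 or higher non-hematologic event occurs, whichever table the site then follows. Nor do that rule's limits show how many patients would meet the conflict, since they count events in any cycle and from any study drug.

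A reader might also take the open-ended Table 8.3 row for a drafting slip. The documents do not settle that. Of the six non-hematologic event groups in Table 8.3, three separate Grade 4 and three do not, and the thromboembolic row deliberately keeps the dose. Grade 4 may have been separated only where a stop was wanted. The three Grade 4 rows also end all study treatment, which Table 8.2 does not, so they agree with Table 8.2 only on pomalidomide.

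Finally, the agent column in Table 8.2 carries a footnote marker with no matching footnote in the available text. It may refer to the NOTE, or a footnote may have been lost when the file was read. That possibility cannot be excluded, but nothing visible resolves the conflict.

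**Conclusion.** The contradiction stands for a Grade 4 non-hematologic event attributed to pomalidomide and without its own pomalidomide row in Table 8.3. It is binding in cycles 1 and 2. It requires that the event resolve within the Section 8.11 limit and that the patient be on 2 mg or more. The difference is a permanent stop against 63, 42 or 21 mg in the next cycle, with re-exposure in the same cycle also possible. The Grade 3 restart thresholds differ as well. This assumes that no missing footnote ranks the rows. How often the conflict would arise is unknown, and no effect on the primary endpoint is shown.

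Table 8.4 might be read as a third conflicting order, because its pancreatitis row (Grade 3 or higher) continues pomalidomide. The documents do not support that for events attributed to pomalidomide. There is a lesser ambiguity: Table 8.2's Grade 4 row lacks the attribution limit of its Grade 3 row and, read alone, would stop pomalidomide for an event due to dexamethasone alone. Section 8.0's attribution language largely answers this, but the row should say so.

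**What to change.** 1. In Table 8.3, limit the other non-hematologic row to Grade 3, with restart at Grade 1 or less or baseline, as in Table 8.2 and Section 8.11. Add a row: any other Grade 4 non-hematologic toxicity at least possibly attributable to pomalidomide, and without its own pomalidomide row in Table 8.3, means permanent discontinuation of pomalidomide. This also covers Grade 4 motor neuropathy and non-rash skin events.
2. In Table 8.2's Grade 4 row, tie each action to attribution. Discontinue pomalidomide permanently if the event is at least possibly attributable to it and has no row of its own in Table 8.3. Consider discontinuing ixazomib, keeping the clinical-benefit exception, if the event is at least possibly attributable to ixazomib and has no ixazomib row of its own in Table 8.2. State that events attributed to dexamethasone alone follow Table 8.4.

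The cost is a wording amendment with no added procedures. The drawback is that some patients whose Grade 4 event resolves lose the option of restarting pomalidomide at a lower dose. Choosing the stricter rule is a clinical decision that the study team must confirm.
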